1 OBJECTIVES AND OUTCOME MEASURES/ENDPOINTS

The aim is to demonstrate the feasibility and acceptability of a course of tDCS sessions for community-based major depression.

1.1 Primary objective

The primary objective is to assess the feasibility of the present trial in terms of study participant retention.

1.2 Secondary objective

The secondary objective is to assess the acceptability of the tDCS sessions.

1.3 Outcome measures/endpoints

Participant retention following enrolment.

1.4 Primary endpoint/outcome

The hypothesis is that there will be participant retention of 70% or greater.

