1.5 Secondary endpoints/outcomes

The hypothesis is that participants will positively endorse the tDCS sessions at the end of the trial as measured by an acceptability questionnaire scale.

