1.7 Table of endpoints/outcomes

Objectives	Outcome Measures	Timepoint of evaluation of this outcome measure
Primary Objective To assess the feasibility of the present trial in terms of participant retention	Participant retention \geq 70%	End of tDCS sessions (visit 21)
Secondary Objective To assess the acceptability of the intervention	Positive endorsement of tDCS sessions as measured by an acceptability questionnaire	End of tDCS sessions (visit 21)

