5.2 Regulatory status of the drug (if applicable): N/A

5.3 Product Characteristics:

The Neuroelectrics StarStim tDCS device does not have CE mark approval for the treatment of major depression. The Soterix tDCS device is a similar device which has CE mark approval for the treatment of major depression (Figure 3).

However, the Soterix tDCS device does not incorporate the EEG electrodes within the device, in contrast to the Neuroelectrics Starstim tDCS device which provides a combined tDCS and EEG system within a simply designed, soft neoprene cap.

The Neuroelectrics Starstim tDCS device is portable and provides an ease of use in a simple design which allows EEG acquisition, which will facilitate its use in the community. The Flow tDCS device is portable and commercially available. Both devices can be programmed to provide the specific stimulation parameters for the study. The primary outcome of the study is to assess the feasibility and acceptability of tDCS sessions within the community.

Clinical efficacy of tDCS treatment for major depression

depression is not the primary outcome for the present study, which is not powered to investigate efficacy. The findings from the present study will be applied to design a multi-site randomised sham-controlled clinical trial, which will be powered to investigate efficacy.

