7 STATISTICAL ANALYSIS PLAN

7.1 Sample size calculation

We will enrol 30 participants with major depression based on a 20% attrition rate to achieve a sample size of 24 participants who will complete the course of treatment, given the exploratory nature of the pilot study.

[figure not shown]

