7.3.2 Primary outcome analysis

The primary outcome analysis is participant retention which will be measured by the number of enrolled participants who do not drop out before the 6 week course of tDCS, divided by the total number of enrolled participants, expressed as a percentage.

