7.3.3 Secondary outcome analysis

The secondary outcome analyses will be the percentage of participants rating the intervention as acceptable at the end of the 6 week course of tDCS. The acceptability scale consists of the question 'How acceptable did you find the tDCS sessions?' with responses ranging from 'Very unacceptable' to 'Very acceptable' on a 7-point anchored Likert scale with the acceptable ratings being from rating 5-7.

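### Retention is stated as a hypothesis of 70% or greater, but retention and acceptability are to be reported as bare percentages with no confidence interval

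*Combined protocol and SAP*

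**What the plan says.** Section 1.1 sets the aim: "The primary objective is to assess the feasibility of the present trial in terms of study participant retention". Section 1.4 turns this into a hypothesis: "The hypothesis is that there will be participant retention of 70% or greater". The table in section 1.7 repeats the 70% figure and places its evaluation at visit 21. Section 1.5 also words acceptability as a hypothesis: "The hypothesis is that participants will positively endorse the tDCS sessions at the end of the trial".

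The analyses are simpler. In section 7.3.2 retention is the number who have not dropped out, "divided by the total number of enrolled participants, expressed as a percentage". In section 7.3.3 acceptability is "the percentage of participants rating the intervention as acceptable at the end of the 6 week course of tDCS", with ratings of 5 to 7 on a seven-point scale counted as acceptable.

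Section 7.1 gives the size: "We will enrol 30 participants with major depression based on a 20% attrition rate", so that 24 finish the course. It justifies this by the exploratory purpose of the pilot and states no precision. The rest of section 7 covers recruitment rate, participant flow, analysis populations and imputation by last observation carried forward (LOCF). Section 5.3 gives the onward use: "The findings from the present study will be applied to design a multi-site randomised sham-controlled clinical trial".

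**The concern.** A hypothesis about a percentage is paired with an analysis that yields one number and nothing about how well that number is known. Followed as written, the plan allows the report to say that the retention hypothesis was met, or not met, without showing the range of true retention rates compatible with the data. With 30 participants that range is wide.

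The result will also be used elsewhere. Designers of the later randomised trial would take the retention figure as an input, and a bare percentage does not tell them how far it could be off. The same applies to acceptability, where the plan also leaves unclear which participants form the denominator.

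**Working it through.** **Inputs.** Enrolled N = 30, attrition 20% and 24 finishing the course (section 7.1); benchmark 70% (sections 1.4 and 1.7); denominator all enrolled (section 7.3.2). Three assumptions are added: a two-sided 95% level, since the documents give none; retention counted at visit 21, as in section 1.7; and, for the 24/30 row only, retention equal to course completion.

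**The plan's own figure.** 24 / (1 − 0.20) = 30, and 30 × 0.80 = 24. Section 7.1 is reproduced. No alpha, power or precision is stated, so there is nothing further to reproduce.

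**Lowest count that meets the benchmark.** 0.70 × 30 = 21.

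**Exact (Clopper-Pearson) interval for x out of n.** Lower limit = 2.5% quantile of Beta(x, n − x + 1). Upper limit = 97.5% quantile of Beta(x + 1, n − x).

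- 21/30 = 70.0%: Beta(21, 10) gives 50.60% and Beta(22, 9) gives 85.27%. Width 85.27 − 50.60 = 34.7 points.
- 24/30 = 80.0%: Beta(24, 7) gives 61.43% and Beta(25, 6) gives 92.29%. Width 92.29 − 61.43 = 30.9 points.

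**Does the method matter?** Wilson 95% intervals are 52.1% to 83.3% at 21/30 and 62.7% to 90.5% at 24/30. One-sided exact 95% lower bounds are 53.5% and 64.3%. At 24/30 the lower limit stays below 70% in each case.

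**What a bare point estimate can hide.** With X binomial (30, p), the probability that X is at least 21 is 35.8% if p = 65%, 58.9% if p = 70% and 93.9% if p = 80%. So true retention of 65% would reach the benchmark about one time in three. This is context only: it describes the point estimate and does not measure the effect of a missing interval. Exactly 21/30 is the least favourable count that meets 70%, with probability 6.8% if p = 80%.

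**Acceptability.** The documents state no expected rate or threshold, so these figures are illustrations. If 24 participants answer at the end of the course (an assumption), 18/24 = 75.0% has an exact 95% interval of 53.3% to 90.2%, and 20/24 = 83.3% has 62.6% to 95.3%.

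The denominator matters. Section 7.7 plans both intention-to-treat and completer analyses, section 7.8 imputes by LOCF, and section 4.6 lists the acceptability questionnaire at baseline. Six missing end-of-course ratings could therefore be filled from earlier ones and counted as data. If the same 83.3% were presented as 25/30, the interval would be 65.3% to 94.4%. That is 29.1 points wide, against 32.6 for 20/24, and the gain in precision would not be real.

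**The case against.** The strongest reply is that this is a small single-arm pilot. Section 1.1 says only that feasibility will be assessed, and 70% works as a point-estimate benchmark. Section 7.3.2 fixes the denominator, so once n/N is reported any reader can compute the interval. No data are lost, no estimate is biased and no decision in the protocol changes. Most of this stands, and it makes the point one of reporting. It does not remove the gap: the document has a dedicated analysis section, that section specifies a percentage and no more, and the level and method are better fixed before results are seen.

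Two further objections stand. First, 24/30 is not a stated retention rate. Section 7.1 speaks of finishing the course, and under section 4.10 a participant can miss sessions without being withdrawn, so retention could differ from completion. Second, section 7.3.2 refers to dropping out before the six-week course while section 1.7 evaluates at visit 21. That is a separate matter to reconcile, and any interval takes its meaning from the definition finally adopted.

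A reader might infer that the trial must rule out retention below 70%, which on the exact 95% interval needs at least 27/30 (lower limit 73.5%; at 26/30 it is 69.3%), and hence that 30 participants are too few. The documents do not support this. No section requires the lower limit to exceed 70%, sets a pass/fail rule or claims confirmatory power.

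**Conclusion.** The concern holds as a reporting gap and should be fixed. Both outcomes are introduced by hypotheses, and both are analysed as percentages with no measure of uncertainty in the readable text. For retention with 30 enrolled, the unreported uncertainty spans 50.6% to 85.3% at 21/30. It spans 61.4% to 92.3% at 24/30, if retention matches the assumed course completion. The imprecision does not hinge on the interval method. These figures rest on a 95% level, full enrolment of 30 and retention counted at visit 21.

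For acceptability the gap is the same, but its size cannot be fixed from the documents, and an interval is meaningful only if N is the number of observed end-of-course responses. The finding does not show that the sample size, the 70% benchmark or the pilot design is wrong.

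**What to change.** - **Section 7.3.2:** report retention as n/N of all enrolled participants, with the percentage and an exact (Clopper-Pearson) two-sided 95% confidence interval. Interpret the 70% figure alongside that interval.
- **Section 7.3.3:** report acceptability as n/N with an exact two-sided 95% confidence interval, where N is the stated number of observed end-of-course responses. Count no LOCF-imputed rating as an observation.
- **Optional:** in section 1.4 describe 70% as a descriptive benchmark (at least 21/30). In section 7.1 give the expected precision, about 61% to 92% at 24/30, labelled as assuming that retention equals course completion.

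The cost is a few sentences of wording and a little more analysis, with no extra participants or data. The downside is a more modest feasibility claim. Sample size and threshold are unchanged.

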1.5 Secondary endpoints/outcomes

The hypothesis is that participants will positively endorse the tDCS sessions at the end of the trial as measured by an acceptability questionnaire scale.

1.6 Exploratory endpoints/outcomes

Exploratory measures:

- i. Trained rater measure of depressive symptoms: Hamilton Rating Scale for Depression (HRSD): The hypothesis is that course of tDCS treatment will improve clinical response as measured by a HRSD score reduction of $\geq 50\%$ following the course of tDCS treatment.
- ii. Self-report measure of depressive symptoms: Patient Health Questionnaire (PHQ-9)
- iii. Trained rater measure of anxiety symptoms: Hamilton Anxiety Scale (HAMA)
- iv. Trained rater measure of manic symptoms: Young Mania Rating Scale (YMRS)
- v. Self-report measure of disability and impairment: Sheehan Disability Scale (SDS)
- vi. tDCS Adverse Events Questionnaire (AEQ)
- vii. Participant acceptability questionnaire scales
- viii. Optional EEG recordings during an eyes-closed resting state for 10 minutes followed by a decision making task (eg. Cheng and Lee, 2015) and an emotional valence categorisation task (eg. Maeoka et al., 2012).

Exploratory outcomes:

- 1) HRSD reduction $\geq 50\%$ following the course of tDCS
- 2) HRSD score ≤ 7 following the course of tDCS
- 3) Improvement in self-reported depressive symptoms as measured by PHQ-9
- 4) Improvement in anxiety symptoms as measured by HAMA
- 5) No significant increase in manic symptoms as measured by YMRS
- 6) Improvement in disability experience as measured by SDS
- 7) Recording of adverse events as measured by the tDCS AEQ
- 8) Measure of neural connectivity using resting state EEG, which has been proposed as potential surrogate outcome measure for clinical applications (Alhaj et al., 2011; Miniussi et al., 2012; Woods et al., 2016). Quantitative EEG analysis of the decision making task (eg. Cheng and Lee, 2015) and emotional valence categorisation task (eg. Maeoka et al., 2012).

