3 PARTICIPANT ELIGIBILITY CRITERIA

3.1 Inclusion criteria

- participants capable of giving informed consent
- male and female
- minimum of 18 years of age
- diagnosis of major depressive disorder based on DSM-5 criteria, with a current depressive episode of at least a moderate severity
- diagnosis will be determined by the Mini-International Neuropsychiatric Interview
- severity will be assessed using the HRSD with a minimum score of 16 indicating at least a moderate severity of symptoms
- taking antidepressant medication or being involved in psychological therapy.

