4.3 The randomisation scheme: N/A

4.3.1 Method of implementing the randomisation/allocation sequence: N/A

4.4 Blinding: N/A

4.5 Emergency Unblinding: N/A

4.6 Baseline data

The baseline data consist of: HRSD, PHQ-9, HAMA, YMRS, SDS, tDCS AEQ, Acceptability questionnaire, EEG (optional) (Appendix 2).

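### HRSD is planned only as two yes/no outcomes, with no summary of change or its SD, although the findings are meant to inform a powered trial

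*Combined protocol and SAP*

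**What the plan says.** Section 1.6 frames the HRSD hypothesis as response: treatment will "improve clinical response as measured by a HRSD score reduction of" at least 50%. The outcome list repeats that cut and adds a second, "HRSD score ≤ 7 following the course of tDCS". Both are yes/no. The neighbouring scales have no cut-off: "Improvement in self-reported depressive symptoms as measured by PHQ-9", "Improvement in anxiety symptoms as measured by HAMA", and a similar entry for SDS.

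The score itself is collected. It sets eligibility (section 3.1: "severity will be assessed using the HRSD with a minimum score of 16 indicating at least a moderate severity of symptoms") and is part of the baseline data in section 4.6.

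Section 7.3 describes analyses of retention and acceptability only. Section 7.7 names an intention-to-treat and a completer analysis, and section 7.8 fills missing values by last observation carried forward. On the use of the results, section 5.3 says: "The findings from the present study will be applied to design a multi-site randomised sham-controlled clinical trial, which will be powered to investigate efficacy". It does not name that trial's endpoint.

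**The concern.** A pilot of this size has few data, and reducing a rating scale to two thresholds uses them inefficiently. The larger issue is what the next trial can take from it. This is a single-arm, open-label study, so it cannot supply a sham response rate or a sham-controlled effect. The spread of HRSD change is one of the more usable quantities it could supply, and two counts do not contain it. The counts also do not show deterioration. A participant who falls from 30 to 16 (14/30 = 46.7%) is reported in the same group as one who does not change and one who gets worse.

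**Working it through.** **Inputs.** From the documents: 30 enrolled, 20% attrition and 24 completers (7.1); entry HRSD of at least 16 (3.1); cuts at a 50% reduction and a score of 7 (1.6). The documents give no response rate, remission rate or SD, so the rates below are assumptions shown as a range.

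**The plan's own figure.** 24/(1 − 0.20) = 30, which reproduces the stated enrolment. It involves no power, effect size or SD.

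**Each cut alone.** For a normally distributed change, a cut with proportion p beyond it retains φ(z_p)²/[p(1 − p)] of the information on the mean. At p = 0.5 this is 0.3989²/0.25 = 0.637, a loss of 36.3%, which is the smallest possible. The loss is 42.4% at p = 0.3, 51.0% at 0.2 and 65.8% at 0.1.

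**The two cuts together.** From a baseline of 16, a score of 7 is a fall of 9/16 = 56.25%, and from a higher baseline the fall is larger. Every remitter is therefore a responder, and the two counts define a three-level outcome. (The nesting holds down to a baseline of 14, where 7/14 = 50%, so a small drop between screening and baseline does not break it.) Treating both cuts as points on one normal scale, which is an approximation, with response rate r and remission rate m:

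retained = φ_r²/(1 − r) + (φ_r − φ_m)²/(r − m) + φ_m²/m

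At 50%/25%: 0.3989²/0.5 + (0.3989 − 0.3178)²/0.25 + 0.3178²/0.25 = 0.318 + 0.026 + 0.404 = 0.749 (from unrounded terms).

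| Assumed response/remission | Loss, response alone | Loss, remission alone | Loss, both together |
|---|---|---|---|
| 60%/30% | 37.8% | 42.4% | 21.9% |
| 50%/25% | 36.3% | 46.1% | 25.1% |
| 40%/20% | 37.8% | 51.0% | 30.3% |
| 30%/15% | 42.4% | 57.4% | 37.7% |
| 20%/10% | 51.0% | 65.8% | 48.5% |

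In participants, 24 completers carry the information of about 24 × 0.749 = 18 at 50%/25%, and of about 24 × 0.515 = 12 at 20%/10%.

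**What a change summary would give.** The 95% half-width for mean change is t(0.975, n − 1)/√n: 0.42 SD at n = 24 and 0.37 SD at n = 30. The 95% CI for the SD is the estimate times √[(n − 1)/χ²]: 0.78 to 1.40 times at n = 24, and 0.80 to 1.34 at n = 30. The n = 30 figures require 30 observed end-of-course scores. Sample size for a continuous endpoint scales with the SD squared, so the n = 24 interval corresponds to 0.777² = 0.60 to 1.403² = 1.97 times the planned size. That is why the SD should be reported with its interval.

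**Effect of carrying the last observation forward.** A dropout with only a baseline score is assigned zero change. If all 6 expected dropouts were of this kind, the mean change would shrink to 24/30 = 0.80 of the completers' mean M. The variance would become about 0.8·SD² + 0.16·M². That inflates the SD if M exceeds √1.25 = 1.12 SD and deflates it otherwise. If HRSD is also scored during the course, the distortion would differ. Appendix 2 was not available here, so visit timing could not be checked.

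**The case against.** The strongest reply is that this is an exploratory outcome in a retention pilot. Section 5.3 describes efficacy as not the primary outcome of a study "which is not powered to investigate efficacy", and no HRSD test is planned, so an efficiency figure for a mean shift answers a question the study does not ask. That stands, and it keeps the severity low. It does not remove the gap, because section 5.3 also gives these findings a planning use.

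Several stronger readings are tempting, and the documents do not support them:

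- *At least a third of the HRSD information is lost.* True of each cut alone, but the plan has two nested cuts. Their joint loss is below a third once response is around 40% or more.
- *The data are discarded.* The scores are collected, and a mean and SD could be computed later. What is missing is a planned summary.
- *The next trial needs the SD.* Only if its endpoint is continuous, and no endpoint is named. A responder endpoint would need rates, and this plan gives the active-treatment rate. A change summary keeps both options open.
- *The cut ranks patients wrongly.* A fall from 16 to 8 counts as response and a fall from 30 to 16 does not, but that is wrong only if absolute points are the right metric. The second patient still scores 16, the entry threshold.
- *HRSD is uniquely neglected.* Section 7.3 gives no analysis for PHQ-9, HAMA or SDS either. Their outcomes are worded as improvement, without a stated summary.

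**Conclusion.** The concern holds in a limited form. Both planned HRSD outcomes are yes/no, and no summary of HRSD change is planned. On mean change, the pair of outcomes loses about 22% to 49% of the information across the assumed rates. This rests on a normal change score and on treating both cuts as lying on one scale. Independently of that model, the two counts cannot give the SD of change and do not show worsening. The consequence for the next trial depends on its using a continuous HRSD endpoint, which the documents leave open. Severity is low, because no primary or secondary conclusion changes.

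**What to change.** In 1.6 and 7.3:

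- Add change in HRSD from baseline to the end-of-course assessment as an exploratory outcome, reported as mean, SD and 95% CI.
- Report the 95% CI of the SD, and the number of participants whose score rose from baseline.
- Base these summaries on participants with an observed end-of-course score, and state how many that is. Show any last-observation-carried-forward version alongside. Observed data can also be selective, so neither version should stand alone.
- Keep response and remission as descriptive counts.
- Summarise change in PHQ-9, HAMA and SDS in the same way.

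The cost is a few lines of text. HRSD is already scored at baseline, and the existing outcomes already require a score after the course, so no new data and no change to the 30 enrolled are needed. The write-up should say that an uncontrolled change informs the SD for the next trial more than the effect size.

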2 TRIAL DESIGN

The trial is a pilot, open-label, single arm trial to determine the feasibility and acceptability of tDCS for major depression within a community-based setting.

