3.2 Exclusion criteria

- treatment resistant depression as defined by a poor clinical response to 2 or more antidepressant trials
- any concurrent psychiatric disorder, including bipolar disorder or any psychotic disorder
- having a significant risk of suicide
- exclusion criteria for tDCS, including having a scalp or skin condition (e.g. psoriasis or eczema); if contact with the scalp is not possible; having metallic implants, including intracranial electrodes, surgical clips, shrapnel or a pacemaker
- history of epilepsy
- history of a seizure which resulted in a loss of consciousness
- neurological disorder or history of migraines

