6.4 Responsibilities

Principal Investigator (PI):

Checking for AEs and ARs when participants attend for tDCS sessions and at follow up.

1. Using medical judgement in assigning seriousness and causality and providing an opinion on whether the event/reaction was anticipated.
2. Ensuring that all SAEs are recorded and reported to the Sponsor.
3. Ensuring that AEs and ARs are recorded and reported to the Sponsor in line with the requirements of the protocol.

Chief Investigator (CI) / delegate:

1. Clinical oversight of the safety of patients participating in the trial, including an ongoing review of the risk / benefit.
2. Using medical judgement in assigning the SAEs seriousness, causality and whether the event was anticipated where it has not been possible to obtain local medical assessment.
3. Immediate review of all SUSARs.
4. Review of specific SAEs and SARs in accordance with the trial risk assessment and protocol.

Sponsor: (NB where relevant these can be delegated to CI)

1. Central data collection and verification of AEs, ARs, SAEs, SARs and SUSARs according to the trial protocol onto a database.
2. Reporting safety information to the CI, delegate or independent clinical reviewer for the ongoing assessment of the risk / benefit.
3. Notifying Investigators of SUSARs that occur within the trial.

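### Exploratory outcome 5 leaves 'significant' undefined; read statistically, a null YMRS test meets it, and in 24 to 30 people that cannot show manic symptoms did not rise

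*Combined protocol and SAP*

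**What the plan says.** Section 1.6 names the Young Mania Rating Scale (YMRS) as a trained-rater measure and states the matching outcome, number 5 in the list, as "No significant increase in manic symptoms as measured by YMRS". Section 4.6 places the scale in the baseline set: "The baseline data consist of: HRSD, PHQ-9, HAMA, YMRS, SDS".

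Section 7.3 describes analyses for retention (7.3.2) and acceptability (7.3.3: "The secondary outcome analyses will be the percentage of participants rating the intervention as acceptable") only. No section gives a test, significance level, margin, threshold or interval for YMRS.

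Section 7.1 enrols 30 people, allowing for 20% attrition, "to achieve a sample size of 24 participants who will complete the course of treatment". Section 7.7 plans an intention-to-treat analysis and a completer analysis, and section 7.8 imputes missing data by last observation carried forward. Section 2 gives the design: "The trial is a pilot, open-label, single arm trial".

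**The concern.** The word 'significant' can be read in two ways, and each leaves a gap. If it means statistically significant, failure to reject the null hypothesis counts as success, and a smaller sample makes success easier. If it means clinically meaningful, the size of rise that would count is not given.

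The other outcomes in the list do not share the first problem. Outcomes 1 and 2 have numeric HRSD criteria. Outcomes 3, 4 and 6 ask for improvement. Outcomes 7 and 8 are recordings or measures with no direction. Among the outcomes that name a direction, only number 5 is met by finding nothing.

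Section 5.3 says the findings will be used to design a later multi-site sham-controlled trial. A statement that outcome 5 was met could carry more reassurance into that design than this sample can give. A test on the mean is also poorly suited to a rise that affects only one or two people.

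**Working it through.** **Inputs from the documents.** 30 enrolled, 20% attrition, 24 completers (section 7.1); single arm, so only within-person change can be estimated (section 2); last observation carried forward (section 7.8).

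**Assumptions.** The documents give no test, significance level, sidedness or SD for YMRS. I assume a paired t-test at 5%, two-sided, with one-sided results also shown. Effects are in SD of change and cannot be converted to YMRS points.

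**Step 1: the plan's own figure.** 24 / (1 − 0.20) = 30, which matches section 7.1.

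**Step 2: chance that a real mean rise is non-significant.** Power = 1 − F(t_crit; n − 1, d√n), where F is the noncentral t distribution function and d is the true rise in SD. For d = 0.3:

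- n=24: t_crit = 2.069, noncentrality 0.3 × √24 = 1.470, power 0.291, missed 71%.
- n=30: t_crit = 2.045, noncentrality 0.3 × √30 = 1.643, power 0.355, missed 64%.

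| True mean rise | n=24, two-sided | n=30, two-sided | n=24, one-sided | n=30, one-sided |
|---|---|---|---|---|
| 0.3 SD | 71% missed | 64% | 59% | 52% |
| 0.5 SD | 35% missed | 25% | 23% | 15% |

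At 0.6 SD, two-sided power is 80% (n=24) or 89% (n=30), so a rise of that size would usually be found.

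**Step 3: effect of carrying baseline forward.** The n=30 figures assume 30 observed end ratings. As a worst case, suppose all six expected dropouts have no post-baseline YMRS and enter as zero change. A true rise of 0.3 SD becomes 0.3 × 24/30 = 0.24 SD on average. By simulation, two-sided power is then about 29%, so the rise is missed about 71% of the time, the same as at n=24.

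**Step 4: what an observed mean change of zero leaves open.** The 95% CI half-width is t_crit/√n: 2.069/√24 = 0.42 SD and 2.045/√30 = 0.37 SD. The interval would still reach +0.42 or +0.37 SD.

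**Step 5: a rise confined to a few people.** This step needs no SD. Let k participants rise by x and the rest not change. The mean is kx/n, the standard error is (x/n)√[k(n − k)/(n − 1)], and x cancels: t = √[k(n − 1)/(n − k)].

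- k=1: t = 1.00 at either n; two-sided p = 0.33.
- k=2: t = √(2 × 23/22) = 1.446 at n=24 and √(2 × 29/28) = 1.439 at n=30; two-sided p = 0.16.
- k=3: p = 0.083; k=4: p = 0.043.

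Spread among the others around a zero average, or unequal rises, only lowers t. One-sided p is 0.16 for k=1 and 0.08 for k=2, so the conclusion for one or two participants is the same.

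**Step 6: what a count would show.** Exact (Clopper-Pearson) 95% CIs:

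| Participants with a rise | of 24 | of 30 |
|---|---|---|
| 0 | 0 to 14.2% | 0 to 11.6% |
| 1 | 0.1 to 21.1% | 0.1 to 17.2% |
| 2 | 1.0 to 27.0% | 0.8 to 22.1% |

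**The case against.** **The point depends on one reading.** No test of YMRS is planned anywhere, so 'significant' may mean clinically notable. That stands: the power figures apply only to the statistical reading. Under the clinical reading the gap is smaller, namely an unstated threshold, and the same replacement closes it.

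**Exploratory outcomes generally lack an analysis.** This is true, and improvement in outcomes 3, 4 and 6 is also left without a test or a size. The difference is that a null result does not meet those outcomes.

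**Individuals with a marked rise have another route.** The adverse-event questionnaire (section 1.6), monitoring at sessions (5.11), the investigator's duty in section 6.4 ("Checking for AEs and ARs when participants attend for tDCS sessions and at follow up") and recording for 3 months after the last session (6.9) all work at participant level. Section 3.2 also excludes "any concurrent psychiatric disorder, including bipolar disorder or any psychotic disorder". These provisions lower the stakes but do not change what outcome 5 says.

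**Stronger readings that a reader might infer.** One is that the sponsor intends to report a null test as absence of manic risk; no section says so. Another is that the trial could not detect any rise; step 2 shows that mean rises of about 0.6 SD or more would usually be detected. A third is that section 5.3 already covers the point, since it describes "the present study, which is not powered to investigate efficacy". That statement concerns efficacy and does not address YMRS.

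**Conclusion.** The point holds conditionally and is worth considering. If 'significant' is statistical, outcome 5 can be met by a result that is weak evidence against small to moderate mean rises: 71% of true 0.3 SD rises missed at n=24, and 64% to about 71% at n=30 depending on how dropouts are handled. It is also no evidence against a rise confined to one or two people when the others average no change. These figures rest on an assumed paired t-test at 5%; a one-sided test lowers the miss rates without removing the problem.

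Priority is low. This is one exploratory outcome, and retention and acceptability are untouched. With a single arm, any YMRS estimate describes change over time and cannot be attributed to tDCS. The post-baseline YMRS schedule is in Appendix 2, which is not in the text reviewed, so the number and timing of later ratings could not be checked.

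**What to change.** Replace outcome 5 in section 1.6, with a matching sentence in section 7.3, by:

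*Mean change in YMRS from baseline to the end of the tDCS course with 95% CI, and the number and percentage (exact 95% CI) of participants whose YMRS rises over the same period by at least an amount the sponsor pre-specifies. Both are reported among participants with a post-baseline YMRS rating, with the number without one stated; any last-observation-carried-forward result is shown alongside. Absence of an increase is not concluded from a non-significant test.*

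The amount is the sponsor's choice and none is proposed here. It should be set in advance, because counting any one-point rise would include rating noise. If Appendix 2 schedules ratings during the course as well as at its end, the sponsor should also state which rating is used for both summaries.

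The cost is one line and one sentence. YMRS is already collected at baseline, and outcome 5 as written already needs a later rating, so no new data should be required, subject to Appendix 2. The downside is a less reassuring statement and the need to fix the amount before the data are seen.
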